We propose to conduct a prospective randomized, and controlled study to compare the effectiveness of PROKERA® plus standard of care (SOC) in the PROKERA® Arm to SOC alone in the Control Arm. Subjects presenting with moderate DED defined as corneal fluorescein staining score of ≥ 3 points out of 9,¹⁴ will be recruited and screened at the two to three participating clinical site(s) in the United States.

Following a run-in period of 2 weeks during which enrolled subjects will use standard dry eye therapies consistent with what is described in the 2007 Report of the International Dry Eye WorkShop (DEWS)^{1,15} [e.g. preservative-free artificial tears, Restasis® (0.05% Cyclosporine A, Allergan, Inc. Irvine, CA), Xiidra® (5% lifitegrast ophthalmic solution, Shire, Lexington, MA), punctal occlusion, etc.], enrolled subjects who still present with signs and symptoms of moderate

[figure not shown]
CLINICAL STUDY PROTOCOL

DED at the screening visit, will continue in the study. Those subjects whose signs and symptoms abate during the run-in period will be discontinued from the study. Subjects who continue in the study will be assigned an appropriate study identification code, and randomized to receive either PROKERA plus SOC or SOC alone.

Subjects assigned to PROKERA plus SOC will have PROKERA inserted into one eye (study eye) and will then restart the SOC treatment for both eyes after randomization. After the PROKERA application for 5 ± 1 days together with SOC, all subjects in the PROKERA® Arm will return to the clinic to have the PROKERA removed and will continue with the SOC treatment for both eyes. Subjects assigned to the Control Arm will start the SOC treatment for both eyes after randomization and will not return to the clinic at 5-day visit. Clinical symptoms will be evaluated by OSDI scale¹⁶ and the Eye Dryness Score (EDS).^{17,18} Signs of corneal epithelial damage will be evaluated by corneal fluorescein staining at the baseline, one month, two months and three months. To assess the potential for a contralateral effect, the above evaluation will also be conducted, for the subject's fellow eye (i.e. non-study eye). In order to eliminate bias, all evaluators will be masked as to the treatment assignment.

STUDY SUBJECTS AND RANDOMIZATION:

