- Presence of other corneal disorder(s) that give rise to reduced corneal sensitivity, such as recurrent herpes keratitis
- Presence of corneal diseases other than dry eye that can disturb the pre-corneal tear film such as epithelial basement membrane dystrophy (EBMD)
- Contact lens wear
- History of recent ocular surgery/trauma, which could affect corneal sensitivity, e.g., corneal transplantation, LASIK
- Presence of cicatricial ocular surface diseases
- A medical or ocular condition, or a personal situation, which in the principal investigator's opinion, is not appropriate for participation in the trial

CLINICAL STUDY PROTOCOL

- Any scheduled or planned ocular or systemic surgery or procedure during the study
- Pregnancy and women who are expecting to be pregnant.
- Current enrolment in another interventional drug or device study or participation in such a study within 30 days of anticipated entry into this study

ENDPOINTS/ OUTCOME MEASURES:
1) EFFECTIVENESS ASSESSMENTS:
Primary Effectiveness Endpoint:

The primary effectiveness endpoint will be defined as the difference in mean change of the total corneal fluorescein staining score of the primary study eye from baseline to 1 month.

Secondary Effectiveness Endpoints

The secondary effectiveness endpoint will be defined as:

- The difference in mean change of the EDS score from baseline to 1 month.
- The difference in mean change of the OSDI score from baseline to 1 month.

Exploratory Outcomes:

- The mean changes of the corneal fluorescein staining score of the primary study eye from baseline at 2 months and 3 months.
- The mean change of the EDS score from baseline at 1 week, 2 months and 3 months.
- The mean change of the OSDI score from baseline at 1 week 2 months and 3 months.
- The same analyses at each time point for the study eye will also be conducted for the subject's fellow eye (i.e. non-study eye)

The Dry eye sign of each eye will be evaluated by the degree of corneal fluorescein staining score. The corneal fluorescein staining score is the sum of three scores by subdividing the entire cornea into upper 1/3, middle 1/3, and lower 1/3, of which each will be graded from 0 (no staining) to 3 (diffuse staining). Thus, corneal fluorescein staining score ranges from 0 to 9, with higher scores representing more severity.

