Dry eye symptoms will be evaluated using the EDS visual analog scale (VAS) to provide a direct assessment of the subject's perception of their current eye dryness symptoms. The VAS has frequently been used for the collection of patient-reported outcomes and has been

CLINICAL STUDY PROTOCOL

commonly used to assess dry eye symptoms in clinical studies. As such, the 2007 report of the International Dry Eye Workshop (DEWS) listed the VAS as a well-defined symptom assessment methodology suitable for use in dry eye clinical trials. Specifically, patient-reported outcomes assessed using the EDS (via VAS) have been used in other dry eye studies and were recently used as the primary symptom endpoint for FDA approval of lifitegrast (Xiidra) for the treatment of the signs and symptoms of dry eye disease.

The Dry eye symptoms will also be evaluated using the validated, 12-item Ocular Surface Disease Index (OSDI) (Allergan, Inc., Irvine, CA), which assesses symptoms of ocular discomfort, effects on visual function, and the impact of environmental triggers. The 12 items are graded on a scale of 0 to 4, where 0 indicates none of the time; 1, some of the time; 2, half of the time; 3, most of the time; and 4, all of the time. The total OSDI score is then calculated on the basis of the following formula: OSDI= [(sum of scores for all questions answered) \times 100]/ [(total number of questions answered) \times 4]. Thus, the OSDI is scored on a scale of 0 to 100, with higher scores representing greater disability.

2) SAFETY ASSESSMENTS:

Adverse events (AEs) during this study are expected to have the same probability of occurrence and of the same magnitude as would be found with subjects with DED and not participating in the study. These could include worsening of the signs and symptoms of dry eye. Some adverse events might be related to PROKERA® placement (adverse device effects -ADEs) which include PROKERA® intolerance, eye irritation, lid swelling and mucus discharge. However, these device related risks are no different in type or frequency when the device is used for dry eye as compared to use of the device for other ocular surface disorders which are already on-label under the FDA 510(k) clearance.

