Safety will be assessed by documenting ADEs, in which the severity, cause and the resolution will be evaluated and reported. The Investigators will determine the severity, assign attribution, and report the event according to the Protocol guidelines. Serious ADEs such as vision threatening conditions may indicate patient withdrawal or termination of the study.

STATISTICAL METHODS:

The primary effectiveness analysis will be conducted on the primary effectiveness measure, the corneal fluorescein staining score change from baseline of the primary study eye, using a mixed-effects model of repeated measures (MMRM) for all randomized eyes within the intent-to-treat (ITT) population, with 1 month being defined as the primary effectiveness endpoint. The MMRM model will utilize Statistical Analysis System's (SAS) PROC MIXED program to perform this analysis and define treatment (PROKERA plus SOC vs. SOC) at 1 month and

CLINICAL STUDY PROTOCOL

treatment-by-month as fixed effects and subject as random effect as well as the baseline corneal fluorescein staining score of the primary study eye as the covariate. The effect of month includes 3 assessments at 1 month, 2 months, and 3 months. The comparison between PROKERA plus SOC and SOC at each month will be conducted, using a model-based t-test procedure, at the significance level of 0.05 (2-sided). The comparison between PROKERA plus SOC and SOC at 1 month will be defined as the primary effectiveness endpoint, whereas the comparisons at 2 months and 3 months will be exploratory analyses.

The OSDI total score change of the primary study eye from baseline over 3 months of the treatment assessment will be analyzed using the same MMRM model described above for the primary effectiveness measure. The comparison between PROKERA plus SOC and SOC at 1 month will be defined as the secondary effectiveness endpoint whereas the comparisons at 1 week, 2 months and 3 months will be exploratory analyses.

To assess the potential for a contralateral eye effect, the above analyses will also be conducted, the subject's fellow eye (i.e. non-study eye) as another exploratory outcome.

SAMPLE SIZE CALCULATION

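### OSDI is analysed by eye and repeated for the fellow eye, but the plan defines only one OSDI total per subject, so as written the fellow-eye run cannot show a contralateral symptom effect

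*Combined protocol and SAP*

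**What the plan says.** All references are to the combined protocol and SAP.

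- **Statistical Methods, OSDI:** "The OSDI total score change of the primary study eye from baseline over 3 months of the treatment assessment will be analyzed". The model is the MMRM specified for staining. Its covariate is the baseline staining score of the primary study eye, and its month effect has three levels (1, 2 and 3 months). The 1-month OSDI contrast is the secondary endpoint; contrasts at 1 week, 2 months and 3 months are exploratory.
- **Statistical Methods, fellow eye:** "To assess the potential for a contralateral eye effect, the above analyses will also be conducted" for the fellow eye, as an exploratory outcome.
- **Effectiveness Assessments, sign:** "The Dry eye sign of each eye will be evaluated by the degree of corneal fluorescein staining score".
- **Effectiveness Assessments, symptoms:** OSDI is a single 0–100 total computed from 12 items by one formula. EDS is a visual analogue scale for the subject's "perception of their current eye dryness symptoms". Neither description mentions an eye.
- **Endpoints:** the primary staining endpoint names the primary study eye. The symptom endpoints do not, for example "The difference in mean change of the EDS score from baseline to 1 month". Exploratory Outcomes adds "The mean change of the OSDI score from baseline at 1 week 2 months and 3 months", again without an eye, and then asks for the study-eye analyses to be repeated in the fellow eye.
- **Study Design:** "Clinical symptoms will be evaluated by OSDI scale" and by EDS, and signs by staining. The evaluation just described is then also to be done for the fellow eye. The device goes into one eye only.

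**The concern.** A contralateral effect can be examined only with a measurement that differs between the eyes. Staining qualifies. A questionnaire total with no eye term does not: the subject gives one answer that reflects both eyes together.

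If the analysis is run as written, a table headed fellow-eye OSDI would show a treatment difference that restates the subject-level result. A benefit confined to the treated eye would appear there as though the untreated eye had improved. A reader could then take an exploratory result as evidence of a contralateral symptom effect when it carries no information on that question.

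Reusing the staining model for OSDI raises two further matters. The covariate carried over is a sign measured in one eye rather than the baseline of the outcome being analysed. The visit levels carried over also omit a visit at which OSDI is to be compared.

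**Working it through.** The plan gives no figure on this point to reproduce, so the main check is textual. The arithmetic that follows uses assumed correlations because the plan states none.

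**1. What the fellow-eye run contains.** For subject i at visit t the outcome is Y_i(t) = OSDI_i(t) − OSDI_i(0). Under the definition in Effectiveness Assessments nothing here carries an eye index. Treatment arm is also a subject-level variable. The only term that could change between the study-eye and fellow-eye runs is the covariate, if fellow-eye baseline staining replaces study-eye baseline staining.

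- With a common covariate, the two runs are the same fit.
- With the staining covariate swapped, the outcome data are still the same and only the adjustment moves.

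A worked example shows the scale (50 subjects, one visit, all values assumed). With baseline OSDI as covariate, both labels give a difference of −14.27 (SE 3.15). With study-eye staining the estimate is −13.87 (SE 3.58), and with fellow-eye staining −14.10 (SE 3.58). The shift of 14.10 − 13.87 = 0.23 comes from the covariate and not from any symptom in the fellow eye.

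**2. Covariate for OSDI.** Take equal variances (set to 1) and define:

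- r = correlation of baseline with follow-up OSDI;
- c = correlation of baseline staining with baseline OSDI;
- d = correlation of baseline staining with follow-up OSDI.

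The residual variance of OSDI change is 2 − 2r − (c − d)² when adjusted for staining, and 1 − r² when adjusted for baseline OSDI. The ratio of baseline OSDI to staining is

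(1 − r²) / (2 − 2r − (c − d)²).

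| c | d | r = 0.3 | r = 0.5 | r = 0.7 |
|---|---|---|---|---|
| 0 | 0 | 0.650 | 0.750 | 0.850 |
| 0.4 | 0.2 | 0.669 | 0.781 | 0.911 |
| 0.6 | 0.3 | 0.695 | 0.824 | 1.000 |

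For example, at c = 0.4, d = 0.2, r = 0.7 the ratio is 0.51 / (0.60 − 0.04) = 0.911. When d = c, the term (c − d)² vanishes and the ratio is that of the top row whatever c is, a reduction of 15–35%.

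Taking d = c/2 and d = c together, the reduction is about 9–35% for c up to 0.4 and 0–35% at c = 0.6. Break-even is at |c − d| = 1 − r. Beyond it there is a small loss: c = 0.7, d = 0.35, r = 0.7 gives 0.51 / (0.60 − 0.1225) = 0.51 / 0.4775 = 1.07.

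**3. Both covariates together.** The residual variance is 1 − (r² + d² − 2rcd) / (1 − c²). At c = 0.6, d = 0.3, r = 0.7, where the swap alone gains nothing, this is 1 − (0.49 + 0.09 − 0.252) / 0.64 = 0.4875. Against 0.51 for staining alone the ratio is 0.956. At c = d = 0, r = 0.3 the ratio is 0.91 / 1.40 = 0.650. In large samples, adding baseline OSDI beside staining cannot raise the residual variance.

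**4. Visit levels.** The month effect has 3 levels (1, 2 and 3 months). The planned OSDI contrasts need 4 (1 week and 1, 2 and 3 months). The model as stated cannot produce the 1-week contrast.

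**The case against.** The strongest reply is that eye-level symptom collection may be intended and specified elsewhere. Study Design lists OSDI, EDS and staining and then extends the evaluation to the fellow eye. The device-placement steps refer to a full study protocol, which is not among these documents, and the study flowchart is not shown. This stands as a limit: the documents support saying that no per-eye score is defined here, and not that none exists.

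Exploratory Outcomes can also be read as repeating only staining for the fellow eye, since staining is the only measure there tied to an eye. That is fair, so the firm contradiction lies in Statistical Methods, with Study Design in support.

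On the covariate, reusing the same model may mean the same structure with the matching baseline. That is plausible, but the text names staining and nothing else, so a clarification is still needed.

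Three stronger readings are tempting and are not supported:

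- **That the 1-month OSDI endpoint is invalid or biased.** The arms are randomized and the subject-level comparison stands. The covariate affects precision only.
- **That controls cannot supply 1-week OSDI.** Study Design says that they "will start the SOC treatment for both eyes after randomization and will not return to the clinic at 5-day visit". This concerns a clinic visit, OSDI and EDS are reported by the subject, and no text says they need a visit. The collection gap is not established; only the missing model level is.
- **That the fellow-eye analysis as a whole fails.** Fellow-eye staining is measured by eye and can address the contralateral question.

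**Conclusion.** The point holds in conditional form. On the documents available, OSDI is one score per subject, while Statistical Methods analyses it by eye and repeats it for the fellow eye. Unless a per-eye OSDI is defined in the full study protocol, that repeat is uninformative about a contralateral symptom effect. This follows from the definition and needs no numerical assumption. EDS lacks an eye term in the same way.

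The covariate gain does rest on assumptions: equal variances, a single-visit approximation to the MMRM contrast, and correlations that the plan does not give. A small loss is possible if staining is strongly related to baseline OSDI but much less to follow-up OSDI, which is a reason to add baseline OSDI beside staining rather than swap it in. The missing 1-week level is a plain mismatch in the text and touches an exploratory comparison only.

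Severity is minor. What is at risk is the misreading of one exploratory result and some precision in a secondary endpoint.

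**What to change.** 1. In Statistical Methods, state that OSDI is a subject-level score and delete the reference to the primary study eye for OSDI.
2. Limit the fellow-eye repeat to staining in Study Design and Statistical Methods, and in Exploratory Outcomes if symptoms were meant there. The alternative is to define a per-eye symptom score: items asked for each eye, a per-eye baseline, and scoring. Apply the same test to EDS.
3. Name baseline OSDI as a covariate in the OSDI model; baseline staining may stay beside it.
4. Add a 1-week level to the OSDI model and state how 1-week OSDI is obtained in both arms, or drop the 1-week between-arm comparison.

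The cost is wording, plus the loss of one exploratory analysis that is uninformative as defined. Baseline OSDI is already needed to compute change. Keeping a fellow-eye symptom analysis would cost more, because a per-eye score would have to be defined and collected. Keeping the 1-week comparison requires 1-week OSDI from both arms.

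### The OSDI model, as written, adjusts for baseline staining and has no 1-week level; the secondary EDS comparison has no stated analysis; OSDI has no eye index but is analysed by eye

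*Combined protocol and SAP*

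**What the plan says.** Statistical Methods defines one repeated-measures model, for change in staining score of the study eye. It has fixed terms for treatment and for treatment by month, a random subject effect, and the "baseline corneal fluorescein staining score of the primary study eye as the covariate". Its time factor is fixed: "The effect of month includes 3 assessments at 1 month, 2 months, and 3 months".

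OSDI change of the study eye then "will be analyzed using the same MMRM model described above for the primary effectiveness measure". Neither a change of covariate nor an added visit is mentioned. The following sentence says that the 1-month OSDI comparison "will be defined as the secondary effectiveness endpoint whereas the comparisons at 1 week, 2 months and 3 months" are exploratory.

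Secondary Effectiveness Endpoints lists two items at 1 month, OSDI and this one: "The difference in mean change of the EDS score from baseline to 1 month". Exploratory Outcomes adds "The mean change of the EDS score from baseline at 1 week, 2 months and 3 months". EDS does not appear in Statistical Methods of the supplied documents.

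Exploratory Outcomes also says: "The same analyses at each time point for the study eye will also be conducted for the subject's fellow eye". Statistical Methods repeats this intention, to look for a contralateral effect. Effectiveness Assessments describes OSDI as a single 12-item total, computed by one formula that has no term for the eye.

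**The concern.** An instruction to reuse a model is adequate only if the model fits the new outcome. Here it fits OSDI poorly in two places. The covariate belongs to another measure, although baseline OSDI must be collected to compute change and will usually predict that change better. The time factor also lacks a level that the plan itself requests. A programmer has to alter something, and the text does not say what.

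For EDS there is nothing to alter, because a named secondary endpoint has no model, covariate or visit structure.

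For the fellow eye the problem is one of meaning. A score taken once per subject cannot differ between that subject's eyes, so repeating its analysis for the fellow eye gives the same result under another label.

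At stake are precision in a secondary endpoint of a 50-subject trial, full pre-specification of both secondary endpoints, and the interpretation of one exploratory analysis. The primary comparison is not at stake.

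**Working it through.** **Coverage.** The plan gives no figure to reproduce on this point. Setting the study-eye and subject-level comparisons between arms that the documents explicitly request against the stated model:

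| Measure | Requested | Covered | Not covered |
|---|---|---|---|
| Staining | 1, 2, 3 months (3) | 3 | none |
| OSDI | 1 week, 1, 2, 3 months (4) | 3 | 1 week |
| EDS | 1 month (1) | 0 | 1 month |
| Total | 8 | 6 | 2 |

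The EDS items at 1 week, 2 and 3 months are left out. Exploratory Outcomes words them as mean changes, not differences in mean change, and Statistical Methods requests no between-arm comparison for them.

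**Precision of OSDI under the literal reading.** The documents give no OSDI SD or correlation, so the inputs are assumptions: baseline SD 1, 1-month SD k, baseline to 1-month correlation r, and staining uncorrelated with OSDI. The 1-month contrast is treated as a single-visit comparison with complete data, so the factors approximate the repeated-measures result.

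- Residual variance of change with baseline staining as covariate: 1 + k² − 2rk.
- Residual variance of change with baseline OSDI as covariate: k²(1 − r²).
- Confidence interval width factor: the square root of the first divided by the second. Each model has one covariate, so degrees of freedom do not differ.

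For k = 1 the ratio simplifies to 2(1 − r)/(1 − r²) = 2/(1 + r):

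| r | Variance ratio | Width factor |
|---|---|---|
| 0.3 | 2/1.3 = 1.538 | 1.240 |
| 0.5 | 2/1.5 = 1.333 | 1.155 |
| 0.7 | 2/1.7 = 1.176 | 1.085 |
| 0.9 | 2/1.9 = 1.053 | 1.026 |

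**Sensitivity to the SD ratio.** For k = 0.8 the factors at r = 0.3, 0.5, 0.7 and 0.9 are 1.411, 1.323, 1.262 and 1.282. For example, at r = 0.3: (1 + 0.64 − 0.48)/(0.64 × 0.91) = 1.16/0.5824 = 1.992, square root 1.411. For k = 1.2 they are 1.146, 1.072, 1.017 and 1.012.

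**Sensitivity to staining.** If baseline staining correlates 0.2 with OSDI change, the literal residual variance falls by the factor 1 − 0.2² = 0.96. With k = 1 and r = 0.3, 0.5, 0.7 the ratios become 1.48, 1.28 and 1.13, so intervals are about 22%, 13% and 6% wider.

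**In power terms.** With k = 1, no staining correlation and the 23 per arm of the sample size section, an OSDI effect with 80% power under own-baseline adjustment would have about 62%, 68% and 73% at r = 0.3, 0.5 and 0.7.

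**Bias.** In a simulation with no treatment effect (25 per arm, 20,000 trials per combination of r and k), the mean error of both estimators was below 0.003 SD throughout, and each model alone rejected in 4.7% to 5.4% of trials. The literal model is valid; it is only less efficient.

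**The case against.** The best defence is that the model was meant as a template. Taken literally it cannot produce the 1-week OSDI comparison, and in the fellow eye it would adjust change for baseline staining of the other eye. The paragraph works only if each outcome brings its own baseline and visits, and then the precision loss is zero. This largely stands: it makes the OSDI part a request to state the covariate and visits, not proof of a wrong analysis. It does not supply an EDS analysis, because the instruction to reuse the model is given for OSDI alone.

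It also stands that every OSDI precision figure rests on assumed SDs and correlations. In addition, the insertion steps under Study Product and Mode of Administration refer to a full study protocol, so an EDS analysis may exist outside the supplied text.

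Some stronger readings are tempting but unsupported:

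- **That OSDI has displaced EDS**, because Statistical Methods speaks of the secondary endpoint in the singular. The list of secondary endpoints uses the same singular above two items, so this is drafting style.
- **That the EDS gap inflates the false-positive rate by a known amount.** Any such figure needs a menu of candidate models, and the documents propose none for EDS.
- **That controls have no 1-week scores.** Study Design says they skip the 5-day visit, but the flowchart is not shown, so what is collected at 1 week is unknown.
- **That EDS is certainly scored once per subject.** It is described as the subject's perception, which does not settle whether the scale is completed for each eye.

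**Conclusion.** The concern holds as a gap in specification for secondary and exploratory analyses. Two of the 8 explicitly requested between-arm comparisons, OSDI at 1 week and EDS at 1 month, fall outside the stated model. EDS at 1 month matters more because it is a secondary endpoint; the 1-week gap is minor.

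For OSDI at 1 month, the literal model costs precision only. Its interval is about 24% to 3% wider for correlations of 0.3 to 0.9, given equal SDs and no staining-OSDI correlation. The loss is larger if the follow-up SD is below the baseline SD (26% to 41% at a ratio of 0.8) and smaller if it is above (1% to 15% at 1.2). Under the template reading it is nil. A reader might infer a biased OSDI result; randomization and the change score rule that out under either reading.

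If OSDI is scored once per subject, as its definition suggests, the fellow-eye OSDI analysis repeats the study-eye result and cannot inform on a contralateral effect. The primary staining analysis is untouched.

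**What to change.** In Statistical Methods:

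1. State that OSDI change and EDS change are each analysed by the repeated-measures model already defined, with the same fixed effects and subject effect, using that endpoint's own baseline as covariate in place of baseline staining.
2. Name EDS at 1 month as a secondary comparison alongside OSDI at 1 month.
3. Add a 1-week level for these endpoints if 1-week scores are collected in both arms; otherwise delete the 1-week comparison.
4. State whether OSDI and EDS are scored per subject or per eye. Limit the fellow-eye analysis to measures scored per eye, with the fellow eye's own baseline as covariate.

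The cost is a few sentences, best written before any outcome data are seen. Baseline OSDI and EDS are already needed to compute change, so no visit, subject or data item is added.

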score and signs such as superficial punctate keratitis (SPK) measured by fluorescein staining, leading to an overall reduction of the mean DEWS severity score from 2.9 ± 0.3 at baseline to 1.1 ± 0.3 at 1 month and 1.0 ± 0.0 at 3 months, respectively (both $p \leq 0.001$). These palliative benefits are correlated with an increase of corneal nerve density measured by *in vivo* confocal microscopy from $12,241 \pm 5,083 \mu\text{m}/\text{mm}^2$ at baseline to $16,364 \pm 3,734 \mu\text{m}/\text{mm}^2$ at 1 month, and $18,827 \pm 5,453 \mu\text{m}/\text{mm}^2$ at 3 months (both $p=0.015$). The increase of corneal nerve density is also correlated with an increase of corneal sensitivity measured by a monofilament in the Bonnet-Crochet esthesiometer. A lasting benefit for more than 3 months after one placement of PROKERA® was also demonstrated in a retrospective study by McDonald et al¹³ in 97 eyes of 84 of patients with moderate to severe DED (DEWS 2-4), of which the majority presented with symptoms of ocular discomfort, blurry vision, ocular pain, redness, and light sensitivity. Most of the cases manifested the ocular sign of SPK due to exposure keratitis, filamentary keratitis, epithelial defect, and neurotrophic keratitis. A single placement of PROKERA® for 5.4 ± 2.8 days leads to notable improvement of DED symptoms and reduction of ocular signs in 74 subjects (88%) as evidenced by notable reduction of the mean DEWS severity score from 3.25 to 1.44 at 1 week, 1.45 at 1 month, and 1.47 at 3 months. Collectively, these data suggest that a single placement of PROKERA® is effective in reducing signs and symptoms of DED for a period lasting at least three months, presumably through a number of mechanisms known for AM including anti-inflammation as well as the resultant benefit to promote the return of corneal nerve density and corneal sensitivity, which has been reported to decline as DED increases its severity.¹²

The present study is designed to further substantiate the effectiveness of PROKERA® in reducing signs and symptoms of DED.

STUDY OBJECTIVES

The primary objective is to evaluate the safety and effectiveness of PROKERA® in reducing signs and symptoms of dry eye disease (DED).

STUDY DESIGN:

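### EDS and OSDI are both listed as secondary endpoints, but the statistical methods cover only OSDI and no rule says how the two symptom scales are to be tested

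*Combined protocol and SAP*

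**What the plan says.** Under Study Objectives: "The primary objective is to evaluate the safety and effectiveness of PROKERA® in reducing signs and symptoms of dry eye disease (DED"). The objective therefore covers symptoms as well as signs. The primary endpoint is corneal staining at 1 month, which is a sign.

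Under Endpoints/Outcome Measures, the plural heading for the secondary endpoints is followed by a singular lead-in, "The secondary effectiveness endpoint will be defined as", and then by two bullets. The first, for EDS, reads "The difference in mean change of the EDS score from baseline to 1 month". The second sets the same comparison, over the same interval, for OSDI.

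The same section supports EDS by noting that scores of this kind "were recently used as the primary symptom endpoint for FDA approval of lifitegrast (Xiidra").

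Under Statistical Methods, the staining comparisons are made "using a model-based t-test procedure, at the significance level of 0.05 (2-sided"). OSDI is then given the same repeated-measures model, and of OSDI alone the text says "The comparison between PROKERA plus SOC and SOC at 1 month will be defined as the secondary effectiveness endpoint". OSDI at 1 week, 2 months and 3 months is exploratory. EDS does not appear in that section. Nowhere do the documents give a testing order, a multiplicity adjustment, a dependence on the primary result, or a rule on whether one or both symptom scales must succeed.

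**The concern.** The two sections disagree on what the secondary endpoint is. The scale with the regulatory rationale (EDS) has no analysis, while the other (OSDI) is named as the single secondary endpoint. A reader cannot tell which of three rules applies: OSDI only, both scales required, or either scale enough.

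This matters more than it would for ordinary supportive secondaries. Because the primary endpoint is a sign, the symptom half of the primary objective rests on these two scales at 1 month. After the results are seen, one could point to the Endpoints section to defend EDS or to Statistical Methods to defend OSDI. As nothing ties the symptom tests to the staining result, a symptom benefit could also be put forward when staining has failed.

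**Working it through.** The plan states no familywise error rate for the symptom endpoints, so there is no figure of its own to reproduce.

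**Inputs**

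- Number of symptom endpoints at 1 month: two (Endpoints/Outcome Measures).
- Level: two-sided 0.05. Statistical Methods states it for staining, and it reaches OSDI through the reference to the same model. For EDS it is an inference, because 0.05 is the only level in the plan.
- Correlation between the two test statistics: not given. Assumed, and varied from 0 to 0.9.

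**Step 1. Each possible rule, with no true effect on either scale**

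- OSDI only, as Statistical Methods reads by itself: one test, error 0.05. No inflation.
- Both scales required: error at most 0.05. No inflation.
- Either scale enough: error above 0.05, computed in step 2.
- Scale chosen after the results are seen, taking the smaller p-value: this is the same event as either scale enough, so it has the same error.

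**Step 2. Error if either scale suffices**

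If independent: 1 − (1 − 0.05)² = 1 − 0.9025 = 0.0975. The upper bound is 0.05 + 0.05 = 0.10.

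If correlated, with Z₁ and Z₂ bivariate normal:

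- any false positive = 1 − P(|Z₁| ≤ 1.96 and |Z₂| ≤ 1.96)
- false positive in the device's favour = 1 − P(Z₁ ≤ 1.96 and Z₂ ≤ 1.96). At correlation 0 this is 1 − 0.975² = 0.0494.

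| Assumed correlation | Any false positive (nominal 0.05) | In the device's favour (nominal 0.025) |
|---|---|---|
| 0 | 0.0975 | 0.0494 |
| 0.5 | 0.0907 | 0.0454 |
| 0.7 | 0.0835 | 0.0417 |
| 0.9 | 0.0704 | 0.0352 |

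**Step 3. Error under a stated rule**

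- Fixed sequence, each step at two-sided 0.05 and only if the step before succeeds: at most 0.05.
- Holm across the two scales (smaller p-value against 0.025, then the other against 0.05): at most 0.05. Its first step at 0.025 each gives 1 − 0.975² = 0.0494 at correlation 0 and 0.0362 at 0.9.
- Putting either rule behind a significant staining result keeps the error over all three tests at or below 0.05, and the staining test itself is unchanged.

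**The case against.** A reader might infer that the plan tests EDS and OSDI each at 0.05 and so gives the symptom claim two chances to succeed. The documents do not support that as a statement of fact. The level "at the significance level of 0.05 (2-sided") is written for staining, reaches OSDI only by reference, and is never attached to EDS. No section says that one scale alone would establish a symptom benefit. If both were required, or if Statistical Methods alone governed, there would be no inflation. This objection stands, and it makes the error rates conditional.

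The wrong claim of concern is a false benefit, so the device-favouring column is the more relevant one. Independence is also the least likely case, since both scales measure dry eye symptoms in the same subjects. Both points are fair. The range therefore runs up to correlation 0.9, and the excess shrinks there but does not vanish.

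The primary inference is sound on this point: one endpoint, one time point and one level, with 2 and 3 months labelled exploratory. In a study of about 50 subjects with a cleared device, reporting secondary p-values as nominal would also be defensible. That is true, but the plan does not say it will do so, and nominal reporting would not settle which scale is the secondary endpoint or supply an analysis for EDS.

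Nor do the documents rank EDS above OSDI for this trial. EDS comes first in the list and has the cited precedent, whereas OSDI has the only described model. The order is for the sponsor to choose.

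**Conclusion.** The inconsistency is established from the text alone: EDS is a secondary endpoint in one section and has no analysis in the other, and no rule governs the two symptom tests. The inflation to about 7% to 10% is conditional. It rests on three assumptions: EDS is tested at two-sided 0.05, either scale suffices (or the better one is chosen afterwards), and the correlation lies between 0.9 and 0. On the same assumptions, a false result favouring the device has a chance of 3.5% to 4.9% against 2.5%.

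The primary analysis, its power and the sample size are untouched. The sponsor should make the correction, because until the sections agree and one rule is fixed, a symptom finding cannot be read as confirmatory.

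**What to change.** In Statistical Methods:

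1. Name both EDS and OSDI at 1 month as secondary endpoints, matching the Endpoints section.
2. Apply the repeated-measures model to EDS with baseline EDS as covariate, and state baseline OSDI as the covariate for OSDI. As written, the model carried over from the primary adjusts for baseline staining.
3. State the time points in each symptom model. The described model has 1, 2 and 3 months, while a 1-week symptom comparison is also planned.
4. Before any results by arm are seen, fix one rule. Test the symptom scales only if 1-month staining succeeds at two-sided 0.05. Then use either a fixed sequence (for example EDS then OSDI, the order in the Endpoints section) or Holm across the two.
5. Report all other p-values as nominal.

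The cost is a short amendment, with no change to primary power or sample size. The price is that neither symptom scale can support a confirmatory claim if staining fails. Under a fixed sequence, the second scale also cannot if the first fails. Under Holm, at least one scale must reach 0.025.
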